### **Confidentiality**

Risks to subject confidentiality will be minimized by storing records with personal identifiers in an office in CEMALB which is locked when unattended by the study coordinators. All samples will be stored with codes only (no personal identifiers). The CEMALB is located in the US Environmental Protection Agency's Human Studies Facility on the UNC campus which has a security guard and limited access 24 hours/day, 7 days/week.

### **Efficacy Measure**

The primary endpoint for efficacy of the nasal allergen challenge will be  $\Delta$ eosinophils/mL of nasal lavage fluid, comparing e-cigarette users to cigarette smokers and non-smokers.

### **Analysis Plan**

For analysis of nasal eosinophil responses, we will use (i) descriptive analysis and (ii) two-sample comparison tests. Specifically, we will use the tabular and graphic methods to describe/explore the basic relationship among the groups. We will then follow up by comparing the  $\Delta$  (post-allergen)-(baseline) responses of the e-cigarette and tobacco smoker groups using two-sample tests, either parametric (t test) or non-parametric (Mann Whitney U), depending on whether the normality assumption is met. We will transform the data to achieve normality if needed. These analyses will be repeated for comparisons of e-cigarette users to non-smokers and for tobacco smokers to non-smokers. In all analyses, criterion for significance will be  $p \leq 0.05$ . [name], the biostatistician for the CEMALB, will oversee all statistical analysis. To support the primary endpoint, we will compare the mean change in NELF eosinophilic cationic protein (ECP) at 4 hours post-allergen challenge from baseline between the e-cigarette users versus tobacco smokers, between the e-cigarette users versus non-smokers, and between tobacco

smokers versus non-smokers using ANCOVA to adjust for baseline NELF ECP. The NELF ECP AUC will be calculated using the trapezoidal rule.

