**b. Patient inclusion and exclusion criteria.**

We will recruit allergic subjects with or without mild asthma, ages 18-50 years, including 15 e-cigarette users, 15 tobacco cigarette smokers, and 15 non-smokers (classification described below). There will be no gender or ethnic restrictions. Allergy skin testing to *D. farinae* will be performed to confirm the presence of allergic sensitization. Only individuals sensitive to house dust mite will be selected for participation. Spirometry will be performed to determine the current level of lung function. Those with an FEV1 (forced expiratory volume in the first second) of at least 80% predicted for age, gender, race, and height and an FEV1 to FVC (forced vital capacity) ratio of at least .75 will be eligible for the study. Subjects for this study will be both mild asthmatic and non-asthmatic healthy volunteers, ages 18-50 years and to include both males and females. Our recruitment goal includes 45 volunteers with at least 50% female subjects and at least a 30% minority representation. It is anticipated that the demographics of our patient population will reflect those of the local university community. Many determinations (e.g. spirometry, allergy skin testing) are made as a part of a separate screening protocol, IRB #98-0799, which is performed to identify subjects for potential participation in experimental challenge protocols such as this one.

Inclusion criteria

1. Specific allergy to house dust mite *D. farinae* confirmed by positive immediate skin test response.
2. Subjects may be enrolled with mild asthma if an FEV1 of at least 80% of predicted and FEV1/FVC ratio of at least .75 (without use of bronchodilator medications for 12 hours), consistent with lung function of persons with mild episodic or mild persistent asthma is demonstrated. For the purpose of this protocol, an asthmatic individual will be defined as having a) positive methacholine challenge with a provocative concentration of methacholine producing a 20% fall in FEV1 (PC20 methacholine) with less than or equal to 10 mg/ml; OR b) physician diagnosed asthma with symptoms and chronic daily therapy consistent with the mild asthma.
3. Subjects will be classified as tobacco smokers, e-cigarette users, or non-smokers according to the following guidelines:

	Tobacco Smokers	E-cigarette Users	Non-smokers
Average cigs/wk	>35 cigs/week	<7 cigs/week	none

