#### Exclusion criteria

1. Any chronic medical condition considered by the PI as a contraindication to the allergen challenge study including significant cardiovascular disease, diabetes requiring medication, chronic renal disease, bleeding disorder, or chronic thyroid disease.
2. Physician directed emergency treatment for an asthma exacerbation within the preceding 12 months.
3. Use of systemic steroid therapy within the preceding 12 months for treatment of an asthma exacerbation.
4. Use of inhaled or nasal steroids, cromolyn or leukotriene receptor antagonists (Montelukast or Zafirkulast) within the past month (except for use of cromolyn exclusively prior to exercise).
5. Subjects who smoke marijuana or use illicit drugs will be excluded.
6. Use of daily theophylline within the past month.
7. Use of nasal medications that might alter the response to nasal allergen challenge including anti-inflammatory and anti-histamine agents within one week of challenge.

8. Inability to withhold inhaled or oral bronchodilator medications for 12 hours prior to allergen challenge.
9. Pregnancy or nursing a baby.
10. Women of child-bearing age who are not using dependable contraception (such as birth control pills, IUD, estrogen patches) or who are not completely abstinent.
11. Nighttime symptoms of cough or wheeze greater than 1x/week at baseline (not during a clearly recognized viral induced asthma exacerbation) which would be characteristic of a person of moderate or severe persistent asthma as outlined in the current NHLBI guidelines for diagnosis and management of asthma.
12. Exacerbation of asthma more than 2x/week which would be characteristic of a person with moderate or severe persistent asthma as outlined in the current NHLBI guidelines for diagnosis and management of asthma.
13. Daily requirement for albuterol due to asthma symptoms (cough, wheeze, chest tightness) which would be characteristic of a person of moderate or severe persistent asthma as outlined in the current NHLBI guidelines for diagnosis and management of asthma. (Not to include prophylactic use of albuterol prior to exercise).
14. Viral upper respiratory tract infection or other acute inflammatory conditions of the nose or paranasal sinuses, such as sinusitis, within 4 weeks of challenge.
15. Any acute infection requiring antibiotics within 4 weeks of challenge.

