#### **Endpoints**

The primary endpoint for this study is  $\Delta$ eosinophils/mL of nasal lavage fluid (post-allergen challenge minus pre-allergen challenge values), comparing e-cigarette users to cigarette smokers and non-smokers. A secondary endpoint will be  $\Delta$ Eosinophilic cationic protein ( $\Delta$ ECP), a marker of eosinophil activation. Exploratory endpoints as well as safety criteria for stopping involvement of an individual in the protocol or suspending the overall study are outlined below.

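### The primary comparison of eosinophil change between three self-selected groups is unadjusted, so a systematic difference in asthma, age or baseline eosinophils could appear as an exposure effect

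*Combined protocol and SAP*

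**What the plan says.** Section 6.1.b classifies subjects as tobacco smokers, e-cigarette users or non-smokers by their own use, 15 per group. It states no matching, stratification or per-group quota for asthma or age. The population is deliberately mixed: "We will recruit allergic subjects with or without mild asthma, ages 18-50 years".

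Under Endpoints, the primary endpoint is post-challenge minus pre-challenge eosinophils/mL of nasal lavage fluid. For it the Analysis Plan says "we will use (i) descriptive analysis and (ii) two-sample comparison tests". The test is "either parametric (t test) or non-parametric (Mann Whitney U), depending on whether the normality assumption is met", with transformation if needed. It is applied first to e-cigarette users against tobacco smokers, and then "These analyses will be repeated for comparisons of e-cigarette users to non-smokers and for tobacco smokers to non-smokers". No covariate is named.

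The same section compares change in ECP between all three pairs, as support for the primary endpoint, "using ANCOVA to adjust for baseline NELF ECP". That model names neither asthma nor age.

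**The concern.** Nothing in the design makes the exposure groups alike. If e-cigarette users, smokers and non-smokers differ systematically in asthma, age or baseline eosinophils, and these affect the eosinophil response, an unadjusted contrast mixes that difference with exposure. The plan has no analysis that would show this for the primary endpoint, yet it applies a 0.05 criterion to every comparison. It already accepts baseline adjustment for ECP and gives no reason for leaving it out of the primary analysis.

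Subtracting baseline does not settle the matter. It removes the baseline level, but not a response that depends on that level, nor regression to the mean.

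**Working it through.** **Inputs from the documents.** 15 per group, 45 in total; outcome is a change score; t or Mann-Whitney tests on three pairs; criterion 0.05 (sidedness not stated, two-sided assumed). The plan gives no power calculation, SD, pre-post correlation or asthma prevalence, so there is no figure of its own to reproduce beyond 3 × 15 = 45. For scale, a two-sided t test with 15 per group has 80% power at a difference of about 1.06 SD.

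**Assumed, not in the documents.** Asthma effect on the response, asthma prevalence by group, baseline difference, pre-post correlation ρ, normal data with equal SDs, and no true exposure effect.

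**1. Asthma.** Spurious difference = asthma effect × (prevalence in one group − prevalence in the other). Simulated t-test rejection, 15 per group, asthma status drawn at random for each subject:

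| Prevalence | Asthma effect (SD) | Spurious difference (SD) | Rejection |
|---|---|---|---|
| 40% vs 40% | 1.0 | 1.0 × 0 = 0 | about 5% |
| 30% vs 50% | 0.5 | 0.5 × 0.2 = 0.10 | 5.7% |
| 30% vs 50% | 1.0 | 1.0 × 0.2 = 0.20 | 7.7% |
| 20% vs 60% | 0.8 | 0.8 × 0.4 = 0.32 | 12.6% |
| 20% vs 60% | 1.0 | 1.0 × 0.4 = 0.40 | 16.1% |
| 10% vs 70% | 1.0 | 1.0 × 0.6 = 0.60 | 32% |

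The first row shows that chance imbalance alone does not inflate the error rate. If the counts are fixed instead of random, 9 vs 3 asthmatics with a 1.0 SD effect gives 13.8%, and 8 vs 5 gives about 5%, although the estimate in the latter is still shifted by 1.0 × 3/15 = 0.20 SD.

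**2. Baseline eosinophils.** Suppose post = ρ × baseline + error, with equal SDs and no exposure effect given baseline. If the groups' baselines differ by D, the expected difference in change is ρD − D = (ρ − 1)D. For D = 0.5 SD:

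| ρ | (ρ − 1) × 0.5 | Rejection, test on change | Rejection, ANCOVA |
|---|---|---|---|
| 0.3 | −0.35 | 12.3% | 5.1% |
| 0.5 | −0.25 | 10.3% | 5.1% |
| 0.7 | −0.15 | 8.3% | 5.2% |

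For D = 1 SD, the test on change rejects in 34.4%, 26.1% and 17.8%.

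**3. Age.** The mechanism is the same as for asthma. No size was calculated.

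**4. Price of adjustment.** Residual degrees of freedom with group, baseline, asthma and age: 45 − 1 − 2 − 3 = 39. Adjusting a two-group contrast for asthma multiplies its variance by 1/(1 − r²), where r is the correlation of group with asthma and r² = (difference in proportions)² × 0.25 / [p(1 − p)], with p the pooled proportion.
- 9/15 vs 3/15: p = 12/30 = 0.40; r² = 0.16 × 0.25 / 0.24 = 0.167; factor 1.20.
- 11/15 vs 3/15: p = 14/30 = 0.467; r² = 0.284 × 0.25 / 0.249 = 0.286; factor 1.40.

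This is before any gain from a smaller residual variance. With equal baselines, ANCOVA has (1 + ρ)/2 of the change-score variance: 0.65, 0.75 and 0.85 at ρ = 0.3, 0.5 and 0.7.

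**The case against.** The strongest case against has four parts.

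- **The plan is not wholly unadjusted.** A reader might infer that no comparison of these groups is adjusted. The documents do not support that: the supporting ECP analysis uses ANCOVA on baseline for all three pairs, and the primary endpoint itself subtracts baseline. The point is limited to the primary eosinophil comparison.
- **Small groups are not the problem.** A reader might infer that 15 per group makes chance imbalance a source of false positives. It does not: with equal prevalence the test rejects in about 5%. Only systematic differences inflate the error, and no passage shows that asthma or age differs by exposure.
- **The design narrows the groups.** All subjects must be skin-test positive to *D. farinae* and meet the FEV1 and FEV1/FVC limits. They must also reach the symptom and nasal-flow thresholds at screening, and then receive their own provocative dose. This partly equalises clinical reactivity, but not the eosinophil response.
- **Adjustment changes the question.** Baseline eosinophils may themselves reflect exposure, so conditioning on them is not neutral in self-selected groups. This stands, and is why the model should support the planned tests and not replace them.

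A reader might also infer that asthma status cannot be obtained because methacholine testing is in no visit list or procedure table. That is unproven: section 6.1.b refers to determinations made under a separate screening protocol and lists them only by example. Visit 0 also takes a medical and medication history.

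**Conclusion.** The concern holds for the primary eosinophil comparison, which is unadjusted in non-randomised groups; the only adjusted analysis is for ECP, on baseline ECP alone. The size depends wholly on assumptions outside the documents. Rejection with no true effect is about 6% to 32% for asthma effects of 0.5 to 1.0 SD and prevalences from 30% vs 50% up to 10% vs 70%. It is about 8% to 12% for a 0.5 SD baseline difference at ρ of 0.7 to 0.3, provided follow-up depends on baseline and not on exposure. Mild imbalance does little to the error rate. These are illustrations of what the plan could not detect, not evidence that the groups will differ. For a pilot, this is a gap worth closing with one supportive analysis, not a reason to discard the planned tests.

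**What to change.** Keep the planned two-sample tests. Add one pre-specified supportive ANCOVA: suitably transformed post-challenge eosinophils/mL on group, the identically transformed baseline, asthma (yes/no) and age. Report all three pairwise contrasts with confidence intervals, described as associations. The pre-challenge lavage at Visit 2 supplies the baseline. Record asthma status explicitly from the Visit 0 history.

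No new procedure is needed. The costs are:
- three degrees of freedom (39 residual);
- a group contrast with variance 1.2 to 1.4 times larger if asthma is strongly imbalanced, before residual-variance gains;
- a model that conditions on a baseline which exposure may have altered, and that cannot remove unmeasured confounding.

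Separately, as an eligibility matter: inclusion 2(b) admits "physician diagnosed asthma with symptoms and chronic daily therapy consistent with the mild asthma", while exclusions 4 and 6 bar recent use of several named controller drugs and exclusion 13 bars "Daily requirement for albuterol due to asthma symptoms". These passages must be reconciled.

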### **Procedures to be Performed**

**Nasal allergen challenge procedure:** Allergen dilutions will be prepared from a 30,000 AU/mL extract solution purchased from Greer® Labs and loaded into nasal actuator devices by a licensed pharmacist in the UNC Investigational Drug Service. Specific lot numbers will be recorded, and CBER will be informed of any lot extract changes. The subject will be instructed to inhale to total lung capacity (TLC). When at TLC, a single-use nasal metered dose pump will then be placed at the base of the subject's nares and activated delivering 100 uL of volume per spray, without an inhalation from the subject. After the correct dose is given, a timer will be set for 10 seconds. At the end of the time the subject will be asked to gently expel excess fluid from the nose into a cup which will be discarded. The technician will spray the solution sequentially distributing between both nares with 0 AU (glycerinated vehicle control), 100 AU (2 sprays or 200 uL of a solution of *Der F* extract of 500 AU/ml), 500 AU (2 sprays or 200 uL of a solution of *Der F* extract of 2500 AU/mL) and 1,000 AU of *Der F* allergen extract (2 sprays or 200 uL of a solution of *Der f* extract of 5000 AU/ml). Once the solution is delivered, the subject will be asked to exhale. The subject will NOT "sniff" the solution. TNSS will be assessed 10 minutes after each dose of the graded nasal dose challenge. Challenge will be stopped when a TNSS of 8 or greater and reduction in PNIF of at least 50% are achieved, or the maximal dose (1,000 AU) is administered.

Subjects will be attended for a minimum of 90 minutes following allergen challenge. An oral exam will be performed prior to each successive dose of allergen and at 30, 60 and 90 minutes post-allergen challenge.

#### **Total Nasal Symptom Score (TNSS):**

Nasal Allergen Symptom score (scale 0-none, 1-mild, 2-moderate, 3-severe):

Sneezing\_\_\_\_, Congestion\_\_\_\_, Nasal Itching\_\_\_\_, Rhinorrhea (Runny nose)\_\_\_\_,

The highest possible score will be 12 and the lowest is 0. A mild score for every criteria is 4, moderate is 8 and severe is 12.

Symptom score descriptor definitions:

**Mild:** Symptom minimally noticeable but would not ordinarily cause you to stop normal activities such as going to work or school and would not keep you from undertaking physical exercise.

**Moderate:** Symptom present but would not ordinarily cause you to stop normal activities such as going to work or school, although it might stop you from doing physical exercise ("working out")

**Severe:** Symptom clearly present and would cause you to consider not going to work or school or seek medical attention (such as calling a health care provider, going to student health, going to the emergency room, or taking medications for these symptoms).

***Follow-up Symptom Score (administered by telephone for post-challenge observation):***

1. On a scale of 0 to 3, with 0=no symptoms, 1=mild symptoms, 2=moderate symptoms, and 3=severe symptoms, please rate the severity of each of the following symptoms:

Sneezing (0-3) \_\_\_\_\_  
Congestion (0-3) \_\_\_\_\_  
Nasal Itching(0-3) \_\_\_\_\_  
Rhinorrhea(0-3) \_\_\_\_\_

2. Do you have any health concerns since we saw you on the day of the challenge?
3. Have you needed to see a doctor for any reason since your last visit?
4. Have you needed to use any over the counter medications?
5. Have you had any specific problems with nasal discomfort, cough, wheezing or have you needed any extra allergy or asthma medicines?

If the symptom score is 6 (out of 12), if any single symptom is scored at 3, or if the answers to questions 2, 3, 4, or 5 are “yes”, then subjects will be offered the opportunity to come back to the laboratory for follow-up assessment.

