##### **Visit 0: Screening allergen challenge day studies:**

1. Consent obtained
2. Urine pregnancy test for females of child bearing potential

3. Vital signs
4. Medical history (including medications) and physical exam (including oral exam, noting the uvula), and a smoking use questionnaire will be obtained.
5. Skin testing for *D farinae* sensitization (unless previously obtained).
6. Baseline spirometry
7. Lavage with normal saline to both nares to clear secretions and prepare for placement of allergen.
8. Total nasal symptom score (TNSS)
9. Peak nasal inspiratory flow (PNIF) measurement
10. Graded nasal allergen challenge using both nares with TNSS after each dose.  
Nasal allergen challenge will be provided in a graded dose fashion 0 AU, 100 AU, 500 AU and then 1,000 AU separated by 10 minutes. Dilutions will be provided by the University of North Carolina Hospitals Investigational Drug Service. Over 10 minutes, symptoms will be monitored and scored. Increasing concentrations of dust mite allergen dilution are deposited into the nose until the TNSS reaches a total of 8 or more (described below) and PNIF is reduced by at least 50%. An oral exam will occur prior to each dose. The cumulative allergen dose producing a TNSS of  $\geq 8$  and reduction in PNIF of  $\geq 50\%$  will be considered the provocative dose of allergen. Failure to achieve TNSS of  $\geq 8$  and reduction in PNIF of  $\geq 50\%$  will result in screen failure.
11. Subjects will be monitored for 90 minutes from the last dose of nasal allergen. Oral and upper airway exam, vital signs and spirometry will be performed at 30 and 60, and a physical exam at 90 minutes. At 90 minutes, if no significant findings on exam and no significant reduction in FEV1 (<10% reduction from baseline), the subject will be discharged.

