#### **Post Nasal Allergen Challenge Telephone Follow up (24 hours after Visit 0)**

Subjects will be contacted for phone call follow-up 24 hours after allergen challenge (see phone script included in the study worksheets section)

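### The telephone follow-up trigger is a total score of exactly 6, so totals of 7 or 8 with no severe symptom do not meet it as written

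*Combined protocol and SAP*

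**What the plan says.** Two sections of 6.1.e give the rule for inviting a subject back after the 24-hour call: Follow-up Symptom Score, and Post Challenge Observations: Reporting. Their wording is the same. The two score conditions read "If the symptom score is 6 (out of 12), if any single symptom is scored at 3". A third condition is a yes to any one of the four further questions numbered 2 to 5, and meeting any of the three leads to an invitation to return for assessment. There are therefore three alternative routes: the total, a single severe symptom, or a yes to one of four questions.

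The telephone items are scored "On a scale of 0 to 3, with 0=no symptoms, 1=mild symptoms, 2=moderate symptoms, and 3=severe symptoms". They are the same four symptoms as in the Total Nasal Symptom Score (TNSS), whose section fixes the anchors of the total: "A mild score for every criteria is 4, moderate is 8 and severe is 12".

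The protocol's other total-score threshold governs the graded challenge and is an inequality both times it appears. Under Visit 0, dosing continues "until the TNSS reaches a total of 8 or more (described below) and PNIF is reduced by at least 50" percent. Under Procedures to be Performed, "Challenge will be stopped when a TNSS of 8 or greater and reduction in PNIF of at least 50% are achieved".

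**The concern.** A rule for escalating care should not switch off as symptoms increase. This one does if followed to the letter: it is met at a total of 6, is not met at 7 or 8 unless one symptom is severe, and is met again from 9 upwards. No reason for that shape is given, and none is plausible.

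At stake is whether a subject with residual symptoms the day after challenge is invited for assessment. After the Visit 0 challenge the next scheduled visit is at least 7 days later, and after the Visit 2 challenge it is 5 to 10 days later. The telephone call is thus the only planned contact in between.

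**Working it through.** **Inputs.** Four symptoms, each scored 0, 1, 2 or 3 (Follow-up Symptom Score). Total from 0 to 12, with 8 when all four are moderate (Total Nasal Symptom Score). Score conditions as written: total = 6, or any item = 3.

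**The plan's own figure.** The maximum is 4 × 3 = 12, which agrees with the stated 12.

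**Where the gap lies.** With no item at 3, the largest possible total is 4 × 2 = 8. Any total of 9 or more must contain a 3 and meets the single-symptom condition. The equality can therefore fail only at totals 7 and 8.

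**Counts.**

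- All patterns: 4⁴ = 256.
- Patterns with no 3: 3⁴ = 81. Patterns with at least one 3: 256 − 81 = 175.
- Total 6 with no 3: four orderings of 2-2-2-0 and six of 2-2-1-1, giving 10.
- Total 7 with no 3: four orderings of 2-2-2-1.
- Total 8 with no 3: one pattern, 2-2-2-2.
- Rule as written: 175 + 10 = 185.
- Rule with *6 or more*: 175 + 10 + 4 + 1 = 190.

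| Total | Patterns | Met as written | Met with *6 or more* |
|---|---|---|---|
| 0–5 | 106 | 40 | 40 |
| 6 | 44 | 44 | 44 |
| 7 | 40 | 36 | 40 |
| 8 | 31 | 30 | 31 |
| 9–12 | 35 | 35 | 35 |
| All | 256 | 185 | 190 |

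In the first row, 81 − 10 − 4 − 1 = 66 of the 106 patterns contain no 3, leaving 40 that do.

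Among the 15 patterns (10 + 4 + 1) that total 6 or more without a severe symptom, the written rule catches 10 and misses 5. These are counts of patterns and not probabilities. The documents give no distribution of telephone scores, so the share of subjects affected cannot be computed.

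**Is the wording corrected elsewhere?** No. Both statements of the rule lack *or more* or an equivalent, and no other section defines the trigger.

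**The case against.** The strongest reply is that nobody would apply the text literally. Beside a severity score and two other escalation triggers, 6 out of 12 reads naturally as a threshold, and staff would hardly invite a subject at 6 and not at 8. That is probably true. It shows that the text differs from the intention, which is a reason to correct it.

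The second reply is that the other questions close most of the gap. Question 5 asks, among other things, about nasal discomfort and any need for extra allergy medicine. Question 2 asks about health concerns and question 4 about over-the-counter products. A missed subject would have at least three moderate nasal symptoms and still answer no to all four questions. That is possible but unlikely, and it limits the practical effect considerably. It does not rescue the score condition, whose only independent role is for subjects who answer no to everything else and have no severe symptom.

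Third, the consequence is slight. The trigger leads only to an offer, a study physician can be reached by telephone at any time, and section f describes nasal symptoms after earlier challenges as typically resolving within 24 to 48 hours. This stands, and it is why the point is minor.

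Fourth, the script that staff use may already be right. The Visit 0 follow-up says "see phone script included in the study worksheets section", and those worksheets are not among the documents. This also stands: the script should be checked, and it cannot be assumed wrong. The Visit 2 follow-up points to a script below, which appears to be the Follow-up Symptom Score section itself.

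A symbol lost in converting the PDF is an unlikely explanation. The sentence is complete in both places, and the greater-or-equal sign survives elsewhere in the protocol.

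**Conclusion.** The concern holds, as a minor error of wording. As written, the total-score condition misses the four 2-2-2-1 patterns and the single 2-2-2-2 pattern, which is 5 of 256, while accepting a lower total of 6. The gap takes effect only when questions 2 to 5 are all answered no. Two assumptions underlie this: the text is read literally, and the intended rule was *6 or more*. The protocol's use of an inequality for its other total-score threshold supports the second.

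The trigger enters no endpoint or analysis, and neither the individual discontinuation criteria nor the study suspension criteria under Safety measures use it. The trial's results are unaffected.

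**What to change.** In section 6.1.e, change the total-score condition to *is 6 or more (out of 12)* under both Follow-up Symptom Score and Post Challenge Observations: Reporting. Check the telephone script in the study worksheets and make the same change there if it repeats the equality.

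The cost is two words in each place. No data item, analysis or visit schedule changes. At most, a few more subjects would be offered a return assessment.
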